(5) Evaluation of the sealing potency of each instrument using indocyanince green (ICG)

- i. Limited to the patients enrolled in Seoul National University Hospital
- ii. ICG (2.5 mg/ml, 1ml at each point) will be injected to the submucosal layer of 2 parts of the lesser curvature (antrum, angle) and 2 parts of the greater curvature (antrum, lower body) of the stomach, at the beginning of the operation under general anesthetia. Presence of leakage will be checked by the laparoscopic view.
- iii. Irrigation during the operation is discouraged as much as possible. Used gauze pieces are preserved in the dark container. The gauze used before LN#1 dissection is collected separately with the gauze used in LN#1 dissection.
- iv. The gauze used before gastrectomy is opened and taken with a SPY® near-infrared camera. Especially, the gauze used in LN#1 dissection is checked separately.
- v. The gauze used after the photographing is put into 200 ml of 70% alcohol and stored for 10 minutes in a shade state to extract ICG from the gauze. Then shoot with a near infrared camera.
- vi. The brightness of the fluorescence in the photographed image is calculated with the image analysis program.

2) Comparison group setting and random assignment method

• This clinical trial was designed to prevent bias that could be involved in assigning registered clinical trial subjects to each group and to identify characteristics of known or unknown subjects that could act as a confounder in evaluating their treatment effects (Eg, demographic characteristics and baseline characteristics) to increase the likelihood of a balanced

- distribution between the two groups, thereby increasing the comparability of the three groups and randomizing to select the three groups from the same group.
- At the time of the clinical trial registration, the subjects who signed the consent form can
 only be identified by the initial name, and the subject will be given a consecutive subject
 screening number by the researcher.

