- After the screening number was assigned, the subjects who satisfied all the inclusion criteria and were not eligible for any exclusion criterion were judged to be suitable for the study. After the insertion of the laparoscopic trocar under general anesthesia, (Eg, after a confirmation of unexpected intraperitoneal or severe adherence do not exist), randomization should be performed. A randomization number (patient ID) will be awarded in a strictly sequential manner in accordance with the randomization table generated by the medical statisticians in advance.
- The randomized method uses a centralized stratified block randomization method to ensure a balanced distribution among the three groups. Institutes and the presence of incision during anastomosis (intracorporeal or extracorporeal anastomosis) will be the stratification factors.
- If a clinical trial subject discontinues clinical trials, the random assignment number assigned to the subject will not be re-used and the subject will not be able to participate in the trial again.
- The trial will be conducted with a single blind spot. Therefore, the practitioner knows the contents of the randomization, but does not disclose the contents of the clinical trial subjects for about 4 weeks after the end of the clinical study.

3) How to use test medical device, combination therapy, reasons for selection when using treatments

Energy-based devices are used in accordance with the manufacturer's manual and the commonly used principles of laparoscopic surgery, and the sites of use during surgery are as described in above 9-1)-(2).

4) Observation items, clinical examination items and observational examination methods

- (1) Primary endpoint: Serum C-reactive protein (CRP) at POD 2
- (2) Secondary endpoint:
 - Blood loss during operation, amount of blood transfusion

- IL-6, IL-10 in serum and ascites at 2-3 hours after surgery and POD 2, 4
- Complication within 30 days after surgery, mortality rate
- At 4 days postoperatively, serum CRP
- Postoperative visual pain score (VAS score)
- The timing of gas release after surgery, start time of liquid diet
- Length of stay, re-admission, emergency room visit and reasons
- Amount of drainage after surgery
- Concentration of triglyceride and amylase in drain
- Amount of Indocyanine green in the peritoneal cavity after surgery, which is injected submucosally before dissection (only in Seoul National University Hospital)
- Number of resected lymph nodes

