- 16) Endocrine: Diabetic ketoacidosis, hyperglycemic hyperosmolar state, Addison's disease, hypothyroidism, etc. Clinically diagnosed
- 17) Stasis: Refers to the case where food is obstructed to pass through the anastomosis, even though there is no evidence of intestinal obstruction, stenosis, leakage, or peritonitis.

- 18) Pancreatic leakage: A case when the amylase level of the drain tube 3 days or more after surgery exceeds 540 U/L, which is three times the normal maximum value of 180 U/L of the normal blood test (1, 3, Check on day 5).
- 19) Chylous ascites: Suspected when the color of a clear white fluid is found with the naked eye, and JP diagnoses that triglyceride is 110 mg/dL.
- 20) Deep Vein Thrombosis
- 21) Central venous infections

9) Evaluation standards, evaluation methods and analysis methods (statistical analysis methods, etc.)

- (1) Primary endpoint: Two days after surgery, serum CRP
- ; Student's t test or ANOVA test was performed by using the mean of CRP value on the second day between the three groups.
- (2) Secondary endpoint:
- Blood loss during operation (ml), amount of blood transfusion (pint); Output-input (ml). Gauze measures the total weight of gauze used during surgery and calculates the difference from the gauze weight measured before surgery. Inhalation volume is calculated by subtracting the amount of 0.9% physiological saline solution applied to the surgical site from the total inhalation volume.
- Serum IL-6, IL-10

Serum IL-6 and IL-10 levels were measured at baseline immediately after general anesthesia and insertion of the trocar. The mean value of serum IL-6 and IL-10 levels 2-3 hours after the operation, the 2nd postoperative day, and the 4th postoperative day are compared by Student's t test or ANOVA test.

- Amount of remaining ICG: Total amount of the remaining ICG will be calculated by the mean value of concentration of the ICG measuring 3 sets for each patient multiplied by 500 (ml) (600 or 700 ml for corresponding cases), and the mean value of the amount of ICG will be compared between each group using t test.

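### Dye spilled at injection is not kept apart from dye leaking through device-sealed tissue, so the ICG sealing endpoint carries device-unrelated noise and a diluted contrast of unknown size

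*Combined protocol and SAP*

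**What the plan says.** All references are to the combined protocol and SAP.

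- **Construct.** Section 11. 1) (5) is headed as an evaluation of each instrument's sealing potency. It applies to one of the two hospitals.
- **Injection.** Step ii: "ICG (2.5 mg/ml, 1ml at each point) will be injected to the submucosal layer of 2 parts of the lesser curvature (antrum, angle"), plus two points on the greater curvature, at the start of the operation. The same step adds "Presence of leakage will be checked by the laparoscopic view". Nothing says what follows if leakage is seen.
- **Collection.** Step iii: "Irrigation during the operation is discouraged as much as possible", and "Used gauze pieces are preserved in the dark container". The one separation described is "The gauze used before LN#1 dissection is collected separately with the gauze used in LN#1 dissection".
- **Measurement.** Step iv: "The gauze used before gastrectomy is opened and taken with a SPY® near-infrared camera". LN#1 gauze is looked at separately. Step v extracts ICG from gauze in 200 ml of alcohol and images it again; step vi derives brightness by image analysis.
- **Endpoint.** Section 11. 4) (2) lists "Amount of Indocyanine green in the peritoneal cavity after surgery, which is injected submucosally before dissection (only in Seoul National University Hospital").
- **Analysis.** Section 11. 9) (2) multiplies a mean concentration from three sets by 500 ml (600 or 700 ml in some cases), and "the mean value of the amount of ICG will be compared between each group using t test". No spill or baseline quantity is subtracted.

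**The concern.** Dye that escapes at the needle does so before the assigned device has touched tissue, so it says nothing about sealing. The leakage check shows that the authors foresaw such escape. Yet no step records it, sets aside gauze used to wipe it, or adjusts for it. With irrigation discouraged, no planned step washes it out either. Spilled dye thus enters the same quantity as dye leaking through sealed tissue.

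This is the one outcome that the plan labels as sealing potency, and the study summary names it among the secondary efficacy measures. Spill common to all arms raises the patient-to-patient variance and adds a constant to every arm's mean. A real difference between devices is then harder to detect and looks smaller in relative terms. The primary endpoint, serum CRP on postoperative day 2, is not affected.

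**Working it through.** **1. The plan's own figure.** The plan gives no effect size, SD, sample size or power for ICG. Its one calculation is for CRP (section 10. 3)): means 11.5 and 8.0, SD 6.6, two-sided alpha 0.05 (two-sided inferred from the stated alternative), power 80%. The t-test calculation gives 56.8, so 57 per group, as stated. 57/0.9 x 3 = 190 against 189 stated, a rounding matter. This figure serves below only as a yardstick.

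**2. Following the dye.**

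| Stage | Text | Is spill separated? |
|---|---|---|
| Injection | 11. 1) (5) ii | Looked for; no recording or action stated |
| Gauze | 11. 1) (5) iii | Split only at LN#1; no set for injection to first device use |
| Imaging, extraction | 11. 1) (5) iv-vi | Gauze used before gastrectomy; no spill set |
| Analysis | 11. 9) (2) | Total by t test; nothing subtracted |

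No stage removes spill or measures it apart.

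**3. Dose.** 4 x 1 ml x 2.5 mg/ml = 10 mg. One point holds 2.5 mg, 25% of the dose. Losing 10% of one point is 0.25 mg.

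**4. Added variance (assumed inputs).** Assume a fraction q of patients spill an amount s, independently of device, and that true seal leakage has SD 0.1 mg (variance 0.01). Spill variance is q(1-q)s². For s = 0.25 and q = 0.2: 0.2 x 0.8 x 0.0625 = 0.0100, which is +100%.

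| s (mg) | q = 10% | q = 20% | q = 30% |
|---|---|---|---|
| 0.1 | +9% | +16% | +21% |
| 0.25 | +56% | +100% | +131% |
| 0.5 | +225% | +400% | +525% |

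**5. Power (assumed inputs).** Let r be spill SD divided by seal-leak SD. The standardised difference shrinks by 1/√(1+r²). Borrowing the CRP planning values (3.5/6.6 = 0.53, 57 per arm):

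| r | Power at 57 per arm | n per arm for 80% |
|---|---|---|
| 0 | 80% | 57 |
| 0.5 | 71% | 71 |
| 1 | 51% | 113 |
| 2 | 24% | 281 |

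The ICG number per arm is not stated. It comes from one hospital and is at most 63.

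**6. Dilution.** Suppose true mean leakage differs twofold and mean spill is m times the lower arm's mean leakage. The observed ratio is (2+m)/(1+m): 1.8 for m = 0.25, 1.5 for m = 1, 1.33 for m = 2.

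**7. Type I error.** Simulating two arms with no device difference, 20 or 40 patients per arm, SD 0.1 mg, and spill of 0.25 mg in 20% or 0.5 mg in 10% or 20%, the t test rejected in about 5% of trials (4.5% to 5.2%). It stays at its nominal level.

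**The case against.** **A false difference or bias.** A reader might infer that an uneven chance distribution of spills could manufacture a difference, or that spill favours one device. Neither is supported. Spill unrelated to the device is balanced in expectation by randomisation, and chance imbalance is what the 5% level already covers (step 7). The operator is not blinded, and the text does not fix whether injection precedes randomisation, so unequal handling of spill cannot be excluded; but nothing in the plan shows it.

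**Large noise as established fact.** The amounts, rates and the 0.1 mg SD are all assumed. No passage says that spill occurs or is mopped with gauze. The injection route is not given either, and backflow into the stomach lumen would not reach the peritoneum. A range of 9% to 525% says that the size is unknown. This objection stands in full.

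**Existing protection.** LN#1 gauze is kept and examined separately, which partly shields that set, although pooled spill could still reach it and the planned comparison is of a total. Section 11. 9-1) allows a rank test when parametric assumptions fail. Relative to a t test on spill-free data, with 0.5 mg spill in 20% of patients the rank test keeps about 44% efficiency against 20% for the t test; with 0.25 mg, 53% against 50%. That eases skew but cannot tell spill from seal leakage.

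**Does the analysed total come from the gauze at all?** The 200 ml extraction read as brightness does not match a concentration times 500 to 700 ml, so setting aside gauze might leave the analysed figure unchanged. This is a fair criticism of a gauze-only remedy. It does not remove the problem: spilled dye enters a gauze measure and a cavity measure alike.

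**Other sealing-related outcomes.** Blood loss, drain volume and drain triglyceride bear on sealing indirectly. ICG is the only outcome so labelled, not the only relevant one.

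**Conclusion.** The point holds as a problem of precision and dilution in one secondary endpoint at one hospital. Followed as written, the plan counts any injection spill into the peritoneal cavity as device leakage. This rests on the absence of any separating step between injection and analysis, and on spill reaching the cavity in at least some patients, which the plan's own check treats as possible.

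The size cannot be computed from the documents. The variance and power tables show how the effect scales under assumed inputs and are not estimates for this trial. The consequence is a possible loss of power and an understated relative difference. Nothing supports a claim of inflated type I error, of an advantage to one device, or of any effect on the primary CRP comparison. Because the change is small, it is worth making despite the unknown size.

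**What to change.** 1. **Section 11. 1) (5) iii:** collect all gauze used before the first activation of the assigned device, including any used to wipe injection leakage, in its own labelled container, and leave it out of the sealing total.
2. **Section 11. 1) (5) ii:** record the injection-leakage check as yes/no, before randomisation where feasible and in any case before first device activation, so that knowledge of allocation or of the later course cannot shape the entry.
3. **Section 11. 9) (2):** prespecify a sensitivity analysis that excludes, or adjusts for, patients with visible injection leakage. Adjustment keeps every patient and is safer if the check could only be recorded after allocation.
4. **Sections 11. 1) (5) v-vi and 11. 9) (2):** reconcile the 200 ml extraction and image brightness with the concentration multiplied by 500 (600 or 700) ml. State which material each of the three sets comes from, so that the set-aside gauze really leaves the analysed quantity.

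The cost is one more container, handled as the LN#1 gauze already is, one case-record field, one extra analysis and a clarification of the text. The main analysis loses no patients. The remaining weakness is that spill not wiped up before dissection stays in the total; items 2 and 3 help with that part only where the spill was visible.

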Absorbed blood in gauze: measure weight of the gauze before the operation then calculate the difference after the operation.

Absorbed amount of blood using inhalator: blood collected in the inhalator bottle will be moved to the 50cc syringe then the amount of blood will be measured. If saline is used for wash out operation region during the operation, that amount will be omitted.

- ② Operation time
- ③ Transfusion volume

(2) Pre- and Post- operation management

- i. Within a month from the date of operation: A laboratory test (CBC, admission panel, CRP, triglyceride, amylase, PT, aPTT), age, medical history, ASA classification, weight, height.
- ii. 1 day before operation: bowel preparation (empty stomach and enema): use of a laxative before operation (Mg. citrate powder intake, suppository bisacodyl 10mg) and suppository glycerin enema and bisacodyl 10mg on the day of operation.
- iii. low molecular weight heparin (LMWH): to prevent DVT, hypodermic medication of 20mg 1 time/ 1day may possible after 2 ~3 days post operatively.

(3) Post-operative evaluation

- PCA (patient controlled analgesia): includes Morphin and fentanyl. When need additional pain control, Nalbuphin (IM) or Fentanyl patch will be used
- 2 From POD 1 to 4, VAS pain score will be measured daily.
- 3 Gas out, day of starting liquid diet will be recorded
- ④ Complications: Within the follow-up period, from the end of operation to 2-3 weeks after discharge, patients will be monitored to check for complications and mortality before POD 30. Complications will be measured by Clavien-Dindo classification. Any reasons for re-admission through an out-patient clinic or emergency during the followup period will separately be recorded.

(4) Laboratory test

i. POD 2, 4: Blood test (CBC, admission panel, CRP, triglyceride, amylase)

ii. POD 2: Amylase and triglyceride test in the drain. Measurement of drainage by 1-3 days after surgery

iii. Cytokines Test:

- Serum IL-6, IL-10: Obtain peripheral blood in 5ml bottle of EDTA bottle : just after the induction of the anesthetia, 2-3 hours after the end of the operation, the 2nd post-operative day, and the 4th post-operative day.
- EDTA bottle is centrifuged at 3000 rpm for 15 minutes as soon as possible after collection. It is divided into 200ul each, and then cytokine assay is asked to clinical research laboratory. On holidays when it is difficult to conduct the test, it is centrifuged, stored at -80 °C and analyzed at the day available.

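### The ICG amount multiplies concentration by an unexplained nominal 500, 600 or 700 ml, although gauze is extracted in 200 ml and the fluid already in it is not counted

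*Combined protocol and SAP*

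**What the plan says.** The bench procedure is in section 11-1)-(5), which applies to Seoul National University Hospital only. The dye is given at four points: "ICG (2.5 mg/ml, 1ml at each point) will be injected to the submucosal layer of 2 parts of the lesser curvature", and at two on the greater curvature. Gauze used before gastrectomy is photographed (item iv). Then "The gauze used after the photographing is put into 200 ml of 70% alcohol and stored for 10 minutes in a shade state" (item v), and the extract is photographed. The last step is "The brightness of the fluorescence in the photographed image is calculated with the image analysis program" (item vi). On other fluid the section says only "Irrigation during the operation is discouraged as much as possible".

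The calculation is in section 11-9)-(2), which starts from concentration: "Total amount of the remaining ICG will be calculated by the mean value of concentration of the ICG measuring 3 sets for each patient". To turn that average into an amount, the section has it "multiplied by 500 (ml) (600 or 700 ml for corresponding cases". The comparison of arms is then stated as follows: "the mean value of the amount of ICG will be compared between each group using t test".

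Blood loss is defined in section 11-1)-(1) as blood in gauze plus suctioned blood. For the gauze part the instruction is: "measure weight of the gauze before the operation then calculate the difference after the operation". No section connects this weight to the ICG calculation.

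**The concern.** An amount equals a concentration times the volume of liquid in which that concentration was measured. Here that liquid is the alcohol plus whatever the gauze carried in. The plan gives one volume for the extraction and three others for the calculation, with no link between them, and leaves the gauze fluid out of both.

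The omission need not be harmless noise. Part of the gauze fluid is blood, and intraoperative blood loss is itself a secondary outcome that may differ by device. The ICG amount is listed in the study summary as a secondary index, and its section presents it as a measure of sealing. If gauze fluid differs between arms, some of that difference passes into the sealing measure with the opposite sign. Even if the arms bleed equally on average, patient-to-patient variation in gauze fluid adds avoidable error.

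The undefined switch to 600 or 700 ml is a second route to error. Section 11-2) describes a single-blind trial in which the practitioner knows the allocation, and nothing says that the volume is chosen without knowledge of the arm.

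**Working it through.** **Step 1. Can the plan's multiplier be reproduced?** The inputs are 200 ml (11-1)-(5), item v) and 500, 600 or 700 ml (11-9)-(2)). No stated step leads from one to the other. Three extracts of 200 ml would make 600 ml, which is one of the alternatives but not the default, and the plan does not say whether the 3 sets are separate extracts or repeat readings. If the extract is really 200 ml, the multipliers overstate the amount by 500/200 = 2.5, 600/200 = 3.0 or 700/200 = 3.5 times, before any dilution. A constant factor of 2.5 cancels in a relative comparison of arms. It would still distort an absolute amount set against the injected dose of 4 x 1 ml x 2.5 mg/ml = 10 mg.

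**Step 2. Effect of the switch.** At the same measured concentration, 600/500 = 1.20 (+20%) and 700/500 = 1.40 (+40%). If more solvent was really used, the concentration falls to match and the product is right. If the choice does not follow the liquid actually present, the amount moves by these percentages, and the error does not cancel when the choice differs between patients.

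**Step 3. Dilution by gauze fluid.** Let A be the true amount, V the nominal solvent volume and b the fluid in the extracted gauze. Under simple dilution:

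- measured concentration = A/(V+b)
- computed amount = A x V/(V+b)
- fraction lost = b/(V+b)

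The documents give no value for b, so 20, 50 and 100 ml are assumptions.

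| Assumed b | V = 200 ml | V = 500 ml | V = 700 ml |
|---|---|---|---|
| 20 ml | 20/220 = 9.1% | 20/520 = 3.8% | 20/720 = 2.8% |
| 50 ml | 50/250 = 20.0% | 50/550 = 9.1% | 50/750 = 6.7% |
| 100 ml | 100/300 = 33.3% | 100/600 = 16.7% | 100/800 = 12.5% |

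**Step 4. Difference between arms at equal true ICG.** The wetter arm reads (V+b_low)/(V+b_high) times the drier arm. For an assumed 20 against 50 ml:

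- V = 200: 220/250 = 0.880, or 12.0% lower
- V = 500: 520/550 = 0.945, or 5.5% lower
- V = 700: 720/750 = 0.960, or 4.0% lower

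**Step 5. When would the ranking reverse?** Only when the wetter arm's true excess of ICG is below (V+b_high)/(V+b_low) - 1. For the same assumed volumes this is 250/220 - 1 = 13.6%, 550/520 - 1 = 5.8% and 750/720 - 1 = 4.2%.

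**Step 6. Check of the remedy.** With V+b as the multiplier, A/(V+b) x (V+b) = A, so the dilution error is zero whichever alcohol volume applies.

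**The case against.** The strongest reply is that the plan never calls 500, 600 or 700 ml a volume of alcohol, and does not hold it fixed. If it is a total liquid volume, or is adjusted case by case for the fluid present, the dilution error shrinks or disappears. That stands, and it is why the dilution result is conditional on a nominal solvent volume. But no such rule is stated, and steps of 100 ml would follow gauze fluid only coarsely.

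It also stands that b is not the intraoperative blood loss. Suctioned blood never enters the extract, the extract appears to hold only gauze used before gastrectomy, and gauze may also hold lymph or irrigation fluid. The gauze used at station 1 is collected separately; if it is also soaked separately, b per extract is smaller again.

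The arithmetic further needs a valid conversion from brightness to concentration. Section 11-1)-(5) stops at brightness, while section 11-9)-(2) starts from concentration. That is a separate gap to close.

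A reader might infer that gauze will be weighed after soaking, so that alcohol is counted as blood. The documents do not support this. They ask for a weight after the operation and are silent on its order relative to the soak; nothing conflicts with weighing first.

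**Conclusion.** Two things hold on the text alone: the extraction and calculation volumes are unreconciled, and fluid in the gauze is not counted. If the multiplier is a nominal solvent volume, the ICG amount is understated by b/(V+b), and more so where the gauze is wetter. The size is unknown. It is 9% to 33% at 200 ml and 4% to 17% at 500 ml for an assumed 20 to 100 ml of gauze fluid. The 20% and 40% shifts from choosing 600 or 700 ml need no assumed gauze volume.

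A reader might go further and conclude that a device that bleeds more will look like the better sealer. The documents do not support that. It requires nearly equal true leakage and a material difference in gauze fluid between arms, and they give no figures for either.

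The endpoint is secondary and measured at one hospital. The CRP primary analysis and the target of 189 patients are unaffected. The change is worth making because it is cheap and removes an error tied to another trial outcome.

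**What to change.** 1. Reconcile the 200 ml in section 11-1)-(5) with the 500, 600 or 700 ml in section 11-9)-(2). Record the alcohol volume actually used for each extract. Set any rule for 600 or 700 ml in writing, applied without knowledge of the arm.
2. In section 11-9)-(2), compute for each extract: ICG amount = concentration x (alcohol volume actually used + weight gain of the gauze in that extract, in ml). If a patient has more than one extract, add the amounts. Blood loss is already reported in ml from gauze weight, so no new conversion is needed.
3. In section 11-1)-(5), state that each extracted gauze set is weighed before soaking, and use the same weight for blood loss.
4. For patients already operated on who have only a total gauze weight taken before soaking, report the corrected amount as a sensitivity analysis. The total is an upper bound for b, because it may include gauze used after gastrectomy, so this version can overcorrect.

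The formula can go into the SAP that section 11-9-1) promises before database lock. The cost is a few sentences and a set-level weighing of gauze that is already weighed, at one hospital.

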Comparison of perioperative outcomes between bipolar sealing device and ultrasonic shears during laparoscopic gastrectomy for early gastric cancer

Version No: 2.1

Date: 2021.7.1

Study Institution: Seoul National University General Surgery
Study in charge: [name]

Study Summary

Study title	(Korean) 위암 환자의 복강경 위절제술에서 에너지 기반 절단기구 간
	의 비교 연구
	(English) Comparison of perioperative outcomes between bipolar
	sealing device and ultrasonic shears during laparoscopic
	gastrectomy for early gastric cancer
Study in charge	[name], associate professor, Seoul National University
	Hospital
Fund support	Medtronic, Inc

	The purpose of this study was to compare the perioperative outcomes								
Study purpose	for patients including inflammatory response of energy-based shears								
	devices used in laparoscopic gastrectomy for early gastric cancer.								
Study design	A randomized comparison between three groups by single blind								
Study design	method.								
Study period	RB approval date ~ 4 years								
Study Subject	Preoperative gastric cancer in the middle or lower part of stomach,								
(Clinical trial	which is expected to be 1 stage.								
drug etc)									
Number of	189 people (3 groups x 63 people)								
subjects									
Vulnerable subjects	No applicable								
	Three energy-based devices were randomly assigned to the group of								
	patients with early gastric cancer in the lower or middle part of								
	stomach, followed by laparoscopic distal gastrectomy by single blind								
	method.								
Study Method	Main analysis group								
	Group A: Ultrasonic shears								
	Group B: Bipolar electrocautery								
	Explorative analysis group								
	Group C: Hybrid devices								
	Primary evaluation index: Serum CRP after 2 days of post-operation								
Validity	Secondary evaluation index: Serum IL-6, IL-10, Amount of								
evaluation	Indocyanine green in the peritoneal cavity after surgery, which is								
	injected submucosally before dissection								

	Second Evaluation Index:						
Safety evaluation	1. Blood loss during surgery						
	2. Complications within 30 days after surgery						
	The purpose of this study was to investigate the perioperative						
Possible effects and outcomes	outcomes of different types of energy-based devices which are						
	considered as the most important factor for laparoscopic gastric						
	cancer and to provide scientific basis for selecting safe and effective						

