This study will comply with the most recent Helsinki Declaration (revised in 2013) and the ICH-GCP, and implementation will begin after IRB approval. The types of surgical instruments used are not blindfolded. Researchers strive to minimize the effects of bias on the results of the research and strive to do their best to ensure the safety of the study subjects.

2) Consent process of the subject

In this study, the doctors included in the collaborators will explain the subject in detail of prescreening research in a language that can be understood by the general public. The description of the study will be performed at the ward at the time of admission to the outpatient clinic or surgery, and the explanatory text and the consent form will be provided to the subject so that they can decide whether to consent for a sufficient time. During the explanation and agreement acquisition process, the research will be voluntary and will attempt to minimize the likelihood of compulsory or unjustified impact by explaining that withdrawal is possible at any time and ensuring standard best practice, whether or not the research is agreed. Consent will be obtained by voluntarily signing the consent form with the subject of the clinical study, and a copy of the statement and agreement will be provided to the subject.

3) Compensation plan of subject

This study was conducted according to standard surgical methods using medical devices that are already widely used and approved, and there are no additional outpatient visits. Therefore, there is no financial compensation for participants participating in research.

As the Cytokine test is not included in routine medical care, the research cost will be charged. In the present study, the postoperative complications were predicted not to exceed the range of complications after general gastric cancer surgery. However, if unanticipated adverse events are considered to be directly related to participation in the study, the reimbursement will be made as prescribed in the insurance under the Clinical Study Subject Compensation Code.

4) Personal information protection plan of research subject

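### The plan does not require the ICG gauze images to be coded or processed without knowledge of the device, nor say how they yield the analysed ICG amount

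*Combined protocol and SAP*

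**What the plan says.** The Study Summary names three secondary efficacy measures, in a line that opens "Secondary evaluation index: Serum IL-6, IL-10, Amount of" and goes on to the ICG left in the peritoneal cavity. Section 11. 4) (2) repeats ICG as one of eleven secondary items. Section 11. 1) (5) presents it as the measure of how well each instrument seals and restricts it to one site: "Limited to the patients enrolled in Seoul National University Hospital".

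In the same section, items iii to v have gauze kept in a dark container, opened and photographed with a near-infrared camera, then "put into 200 ml of 70% alcohol" and photographed again. Item vi closes the procedure: "The brightness of the fluorescence in the photographed image is calculated with the image analysis program".

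On masking, section 11. 2) says "The trial will be conducted with a single blind spot" and continues "Therefore, the practitioner knows the contents of the randomization"; the allocation is withheld from the patient. Section 13. 1) adds "The types of surgical instruments used are not blindfolded".

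Section 11. 9) (2) defines the analysed quantity as a mean ICG concentration over three sets per patient, "multiplied by 500 (ml) (600 or 700 ml for corresponding cases"), compared between groups by t test. The visit schedule likewise lists an ICG concentration, taken during the operation.

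**The concern.** A program computes brightness from whatever image, region and threshold it is given. The plan fixes none of these, nor the camera distance or exposure, and does not require that the person choosing them be unaware of the device. In a trial that masks only the patient, a small habit in handling or reading that differs by device would be indistinguishable from a difference in sealing. The result at stake is the trial's direct comparison of sealing. Section 8. 2) also states an expectation that the bipolar device will do better on inflammation, so an ICG result in the same direction would be easier to defend if the images had been read under a code.

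**Working it through.** **1. Is there a safeguard elsewhere?** Section 11. 1) (5) iii to vi names no operator, code, region, threshold or exposure rule. Sections 11. 2) and 13. 1) describe the practitioner and the instruments; neither mentions the person who runs the image program. Section 9-1) plans a blinded data review, but it is directed at exclusions and missing data, not image reading. The safeguard is therefore absent, and the documents are silent on what the operator knows.

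**2. The plan's own figures.** No SD, effect size, power or number of patients is given for ICG. The only sizing is for CRP, in section 10. 3): difference 11.5 − 8.0 = 3.5, SD 6.6, two-sided 5%, power 80%. An exact two-sample t calculation gives 56.8, so 57 per group, as stated. Then 57 / 0.9 × 3 = 190, against the stated 189 = 3 × 63. This reproduces and is not in question. Its use here is to cap the ICG numbers at 63 per arm, a limit reached only if the second site contributed nobody to those arms.

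**3. Illustration of size. The shift, the SD scale and the number per arm are all assumptions.** Suppose there is no true difference and handling shifts one arm by d SD. With n per arm:

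SE = √(2/n) in SD units; type I error = Φ(d/SE − 1.96) + Φ(−d/SE − 1.96).

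For n = 40, SE = √(2/40) = 0.224. With d = 0.1, d/SE = 0.45 and the error is 7.3%. With d = 0.2, d/SE = 0.89 and the error is 14.5%. If the coefficient of variation were 50%, these shifts would be 5% and 10% of the mean (0.1 × 50% and 0.2 × 50%).

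| n per arm (assumed) | d = 0.1 | d = 0.2 | d = 0.3 |
|---|---|---|---|
| 20 | 6.2% | 9.7% | 15.8% |
| 30 | 6.7% | 12.1% | 21.3% |
| 40 | 7.3% | 14.5% | 26.9% |
| 63 (ceiling) | 8.7% | 20.2% | 39.1% |

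These figures show what a shift would do if it existed. They are not evidence that one exists. Masked reading would remove only the part of the shift that arises in reading.

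**4. From photograph to analysed amount.** Section 11. 1) (5) gives brightness, from gauze photographed both before and after extraction in 200 ml, without saying which image supplies the value. Section 11. 9) (2) gives concentration × 500, 600 or 700 ml. No conversion from brightness to concentration is stated, and the three sets are not defined. If the concentration is that of the 200 ml extract, multiplying by 500 to 700 overstates the amount by 500/200 = 2.5 to 700/200 = 3.5 times. No rule says which cases take 600 or 700 ml, and that choice alone moves a patient's value by 600/500 = 1.2 or 700/500 = 1.4 times. If the volumes refer to something else, the text does not say what.

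**The case against.** The strongest reply is that the point rests on silence. Brightness is calculated by software, not scored by eye, and no sentence places an unmasked person at the program. That stands: a reader might infer that the images are read by staff who know the device, but the statements on blinding concern the practitioner and the instruments and cannot be stretched to an unnamed analyst. A reader might also take the Medtronic funding, with that company's Ligasure as the bipolar device (section 9), as a sign of bias; it shows none.

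Second, the size of any bias is unsupported. That stands too. No document gives an ICG spread, a site split or a reading shift, so a claim that the false-positive rate is raised to a particular level would go beyond the text.

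Third, coding files leaves part of the problem untouched. The surgeon knows the device and controls gauze use and irrigation before any photograph is taken. How gauze is laid out matters for the first photograph and less clearly for the extract. Nor can capture settings be fixed after the event: this version is dated July 2021, and section 11. 9) (2) describes a device change under an approval of July 2018, so some images may already exist. All of this limits the benefit, but choice of image, region and threshold can still be masked.

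Finally, ICG is a single-site item among eleven secondary ones. That bears on weight, although its place in the Study Summary sets it above most of the others.

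**Conclusion.** The point holds as a cheap improvement to one secondary endpoint. The plan allows the ICG images to be processed with knowledge of the device and leaves the operator's choices open. It does not establish that this happens, so the bias is possible and of unknown size. The type I error figures of about 6% to 20% for shifts of 0.1 to 0.2 SD rest entirely on assumed shifts and assumed numbers per arm (20 to 63). The primary endpoint, serum CRP on day 2, is a laboratory value and is unaffected, and no sample size changes.

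The mismatch between sections 11. 1) (5) and 11. 9) (2) needs no assumption about anyone's conduct: as written, it is undefined how the photographs produce the analysed amount. It is at least as serious as the masking gap and should be settled with it.

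**What to change.** In section 11. 1) (5), state that:

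- image files carry a code with no device name;
- region and threshold are fixed before any reading, and camera distance and exposure are fixed for future cases;
- existing staff calculate brightness from the coded files and lock the values before allocation is merged;
- any files already stored are coded and re-read under the same rules, with a note that their capture settings could not be standardised.

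Reconcile this section with 11. 9) (2). State which photograph is used, how brightness becomes concentration, what the three sets are, which volume multiplies the concentration, and when 600 or 700 ml applies.

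The cost is a short protocol addition and a small labelling and re-reading workload, with no added patient procedure. Calling it low is a judgement, since the documents give no costs. The report should acknowledge that gauze use and irrigation in theatre remained unmasked.
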